6.1 Investigational Medicinal Product (IMP)

An investigational medicinal product is a pharmaceutical form of an active substance or placebo being tested or used as a reference in a clinical trial, including products already with a marketing authorization but used or assembled (formulated or packaged) in a way different from the authorized form, or when used for an unauthorized indication, or when used to gain further information about the authorized form.

The IMP in this study is Pembrolizumab. It will be delivered to the participating center free of charge. Details on the distribution will be described in a specific operation procedure with appropriate forms attached. All other concomitant medical treatment will be prescribed by the treating physician, as this prescription is within the framework of standard of care.

The relevant information on the drug characteristics, storage, application, mode of action and adverse reactions is included in the respective and current Investigator's Brochure and pharmacy manual provided in the ISF.

The investigator will ensure that the study medication is used only in accordance with the protocol.

6.1.1 Supply of pembrolizumab

Pembrolizumab will be supplied by MSD and will bear a label with the identification required by local law, the protocol number, drug identification and dosage as well as the statement "For Clinical Trial Use Only". The packaging and labeling of the study medication will be in accordance with MSD standards and local regulations. All the requirements of Annex 13 of the Good Manufacturing Practices guideline for labeling investigational drug will be fulfilled.

Upon arrival of study medication the local pharmacy will check the IMP for damage and verify proper identity, quantity, integrity of seals and temperature conditions, and report any deviations or product complaints to the Sponsor upon discovery. The study medication must be stored according to the details on the product label. The drug label indicates the storage temperature. The relevant information on the drug characteristics, storage, application, mode of action and adverse reactions is included in the respective and current Investigator's Brochure of pembrolizumab.

The investigator will ensure that the study medication is used only in accordance with the protocol.

6.1.2 Documentation

The responsible pharmacist will maintain records of the inventory at the site, the use for each patient and delivery, storage and destruction. The investigator will also maintain records that adequately document that patients were provided the doses specified in the protocol and the responsible pharmacist will reconcile all study medication received from the central pharmacy.

The date, time and amount will be documented in the eCRF by the investigator.

6.2 Preparation and Administration of Pembrolizumab

6.2.1 Drug Name, Formulation and Storage

Drug name:pembrolizumab (MK-3475) CAS number 1374853-91-4Dosage:100 mg/vial

Formulation:

- Pembrolizumab Solution for Infusion is provided in Type I glass vials intended for single use only.
- Pembrolizumab Solution for Infusion 100 mg/vial is a liquid DP (manufactured using the fully formulated DS with L-histidine as buffering agent, polysorbate 80 as surfactant, and sucrose as stabilizer/tonicity modifier).

Reconstitution: The liquid drug product can be further diluted with normal saline or 5% dextrose in the concentration range of 1 to 10 mg/mL in intravenous (IV) containers made of polyvinyl chloride (PVC) or non-PVC material. Reconstituted vials should be immediately used to prepare the infusion solution in the IV bag and the infusion solution should be immediately administered.

Appearance: clear to opalescent solutions, essentially free of visible particles.

Labelling:Labelling of study drug will be in accordance with German GCP-V §5 and other applicable national regulations in the German Drug Law (AMG) and GCP-V in effect.

Storage:

- Pembrolizumab (MK-3475) solutions may be stored at room temperature for a cumulative time of up to 6 hours. This includes room temperature storage of reconstituted drug product solution in vials, room temperature storage of admixture solutions in the IV bags and the duration of infusion.
- In addition, reconstituted vials and/or IV bags may be stored under refrigeration at 2 °C to 8 °C for up to 18 hours. If refrigerated, allow the vials and/or IV bags to come to room temperature prior to use.
- From a microbiological point of view Pembrolizumab (MK-3475) has to be used immediately once the vial has been opened. If not used immediately, the responsibility for storage time and storage conditions lie within the handler.

6.2.2 Route of Administration

Pembrolizumab is administered as an i.v. infusion with 200 mg fixed dose corresponding to 2 vials (100 mg/ vial). The treatment interval is q3w (Day 1 of each 21 day cycle). Pembrolizumab (MK-3475) infusions should be administered in 30 minutes, with a window of -5 and +10 minutes, using an infusion pump. A central catheter is not required for infusion; however if a subject has a central venous catheter in place, it is recommended that it be used for the infusion.

The following infusion set materials are compatible with Pembrolizumab (MK-3475):

- o PVC Infusion set that is plasticized using DEHP
- PVC and tri-(2-ethylhexyl) trimellitate (TOTM) infusion set
- Polyethylene lined PVC infusion set
- PVC Infusion set that is plasticized using Di-2-ethylhexyl Terephthalate (DEHT)
- Polyurethane set

*Contact Sponsor for materials not listed above

• A sterile, non-pyrogenic, low-protein binding 0.2 to 5 µm in-line filter made of polyethersulfone (PES) must be used during administration to remove any

adventitious particles. If the infusion set does not contain 0.2 to 5 μ m in-line filter, it is recommended to use 0.2 to 5 μ m add-on filter which may contain an extension line (Note: the materials of the extension line and filter should be as mentioned above).

- Attach the infusion line to the pump and prime the line, either with normal saline (at least 25 mL) or with infusion solution as per local SOP, before starting the infusion.
- Infuse Pembrolizumab (MK-3475) over approximately 30 minutes, with a window of -5 and +10 minutes, through a peripheral line or indwelling catheter.
- In case of infusion reactions, infusion rate may differ:
 - Whenever possible, the lowest infusion rate should be used that will allow completion of the infusion within the 30 minutes
 - Maximum rate of infusion should not exceed 6.7 mL/min. through a peripheral line or indwelling catheter. However, when it is necessary to infuse a larger volume (i.e., 250 mL), the flow rate may go as high as 10 mL/min (maximum) in order to keep the infusion within the window as defined above.
- Ensure the entire contents of the bag are dosed and all remaining drug solution in the line is administered according to institutional guidelines for saline flushing.

6.2.3 Infusion reactions – Course of action and premedication

Infusion reactions – although rare – may occur during the administration of Pembrolizumab. Patients experiencing infusion reaction need to be treated appropriately as detailed in Table 2.

In case of grade 2 infusion reactions patients may be prophylactically pre-medicated upon subsequent study drug applications. Detailed guidelines for handling of infusion reactions are provided in Table 2.

6.2.4 Compliance

The Investigator or a pharmacist or other appropriate individual, who is designated by the local Principal Investigator, should maintain records of the inventory at the site, the use for each patient and delivery, storage and destruction. Investigators should maintain records that adequately document that patients were provided the doses specified in the protocol and reconcile all investigational product(s) received from the sponsor.

The investigator should ensure that the investigational product(s) are used only in accordance with the protocol.

The investigational product(s) should be stored as specified by the Sponsor and in accordance with applicable regulatory requirements.

6.3 Dose Modifications

6.3.1 Dose Modification and Discontinuation of pembrolizumab for adverse reactions Dose modifications in terms of dose reductions are not allowed in this study. Dose modifications in terms of pausing of treatment or discontinuation may be required due to AEs.

Adverse events (both non-serious and serious) associated with pembrolizumab exposure may represent an immunologic etiology. These adverse events may occur shortly after the first dose or several months after the last dose of treatment. Pembrolizumab must be withheld for drug-related toxicities and severe or life-threatening AEs as per Table 1 below. See Section 6.3.2 for supportive care guidelines, including use of corticosteroids.

Toxicity	Hold Treatment For Grade	Timing for Restarting Treatment	Discontinue Treatment Discontinuation
Diarrhea/Colitis	2-3	Toxicity resolves to Grade 0-1	Toxicity does not resolve within 12 weeks of last dose or inability to reduce corticosteroid to 10 mg or less of prednisone or equivalent per day within 12 weeks
	4	Permanently discontinue	Permanently discontinue
AST, ALT, or 2 Increased Bilirubin 3-4	2	Toxicity resolves to Grade 0-1	Toxicity does not resolve within 12 weeks of last dose
	3-4	Permanently discontinue (see exception below) ^a	Permanently discontinue
Type 1 diabetes mellitus (if new onset) or Hyperglycemia	T1DM or 3-4		Resume pembrolizumab when patients are clinically and metabolically stable

Table 1: Dose Modification Guidelines for Drug-Related Adverse Events: For more details please see
 6.3.2 'supportive measure guidelines'.

AIO-Studien-gGmbH

Toxicity	Hold Treatment For Grade	Timing for Restarting Treatment	Discontinue Treatment Discontinuation
Hypophysitis	2-4	Toxicity resolves to Grade 0-1. Therapy with pembrolizumab can be continued while endocrine replacement therapy is instituted	Toxicity does not resolve within 12 weeks of last dose or inability to reduce corticosteroid to 10 mg or less of prednisone or equivalent per day within 12 weeks
Hyperthyroidism	3	Toxicity resolves to Grade 0-1	Toxicity does not resolve within 12 weeks of last dose or inability to reduce corticosteroid to 10 mg or less of prednisone or equivalent per day within 12 weeks
	4	Permanently discontinue	Permanently discontinue
Hypothyroidism	2-4	Therapy with pembrolizumab can be continued while thyroid replacement therapy is instituted	Therapy with pembrolizumab can be continued while thyroid replacement therapy is instituted
Infusion Reaction	2 ^b	Toxicity resolves to Grade 0-1	Permanently discontinue if toxicity develops despite adequate premedication
	3-4	Permanently discontinue	Permanently discontinue
Pneumonitis	2	Toxicity resolves to Grade 0-1	Toxicity does not resolve within 12 weeks of last dose or inability to reduce corticosteroid to 10 mg or less of prednisone or equivalent per day within 12 weeks
	3-4	Permanently discontinue	Permanently discontinue
Renal Failure or Nephritis	2	Toxicity resolves to Grade 0-1	Toxicity does not resolve within 12 weeks of last dose or inability to reduce corticosteroid to 10 mg or less of prednisone or equivalent per day within 12 weeks
	3-4	Permanently discontinue	Permanently discontinue
All Other Drug- Related Toxicity ^c (e.g. skin	3 or Severe	Toxicity resolves to Grade 0-1	Toxicity does not resolve within 12 weeks of last dose or inability to reduce corticosteroid to 10 mg or less of prednisone or equivalent per day within 12 weeks
related AEs, such as toxic epidermal necrolysis)	4	Permanently discontinue	Permanently discontinue

Note: Permanently discontinue for any severe or Grade 3 drug-related AE that recurs or any lifethreatening event.

^{1a} For patients with liver metastasis who begin treatment with Grade 2 AST or ALT, if AST or ALT increases by greater than or equal to 50% relative to baseline and lasts for at least 1 week then patients should be discontinued.

^{2b} If symptoms resolve within one hour of stopping drug infusion, the infusion may be restarted at 50% of the original infusion rate (e.g., from 100 mL/hr to 50 mL/hr). Otherwise dosing will be held until symptoms resolve and the subject should be pre-medicated for the next scheduled dose; Refer to

- Infusion Treatment Guidelines for further management details.

^c Patients with intolerable or persistent Grade 2 drug-related AE may hold study medication at physician discretion. Permanently discontinue study drug for persistent Grade 2 adverse reactions for which treatment with study drug has been held, that do not recover to Grade 0-1 within 12 weeks of the last dose.

Dosing interruptions are permitted in the case of medical / surgical events or logistical reasons not related to study therapy (e.g., elective surgery, unrelated medical events, patient vacation, and/or holidays). Subjects should be placed back on study therapy after not more than 6 weeks after the last dose, unless otherwise discussed with the

Sponsor. The reason for interruption should be documented in the patient's study record.

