2.5 Secondary endpoints

- disease free survival
- overall survival

2.6 Exploratory endpoints:

- prognostic value of tumor shrinkage
- prognostic value of inflammatory infiltrates in and around the resected tumor
- serum- and tumor tissue cytokine concentrations
- multi-OMICS tissue analysis approach for markers and mechanisms

3 Overview of Study Design and Dosing Regimen

The study is designed as an open-label, single arm, prospective, monocentric, phase II study of pembrolizumab in a neoadjuvant setting in patients with non-small cell lung cancer of Stage II/IIIA suitable for surgery.

During the treatment phase, patients will receive intravenous pembrolizumab 200 mg q3wks. for 2 cycles or occurrence of non-tolerable toxicity. After completion of immunotherapy lobectomy or bilobectomy with curative intent is scheduled. After end of protocol treatment, patients will be treated individually according to local standards.

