3.1 Treatment Phase

After screening, patients will be treated with Pembrolizumab every 3 weeks for 2 cycles. A non-invasive tumor assessment by PET-CT will be performed before neoadjuvant treatment and before curative intent surgery. If tumor progression or non-tolerable toxicity is noted during immunotherapy, an End of Treatment (EOT) visit will be performed and the patient will enter the follow-up phase.

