3.1.1 Surgery

Surgery is the standard treatment in the neoadjuvant treatment approach and not a study specific procedure. The procedure of standard lobectomy/bilobectomy with systematic lymph-node dissection is well described in all manuals of thoracic surgery. In brief, patients undergo general anaesthesia and endobronchial double-lumen intubation. Blood pressure, heart rate, electrocardiographic trace, respiratory frequency and oxygen saturation are monitored continuously throughout the operation by an anaesthesiologist. Thoracotomy is usually performed through the fourth or fifth intercostal space. Vascular and bronchial structures at the level of the hilum are prepared and resected along with the corresponding lobe and lymph node containing fatty tissues. A radical systematic lymph node dissection accomplishes a standard lobectomy procedure. Vessels can be closed by ligation, suture or stapler. The bronchus can be closed by suture or stapler. Depending on the anatomical consideration of the interlobar fissure and the different techniques in use, the division can be performed at the beginning or the end of the surgery and can be done by

stapler, cautery or any other technique. Surgical technique for closure of vessels and bronchus, and the different techniques of parenchymal sparing have to be described for each patient in the OP-records. In special cases video-assisted thoracic surgery (minimal-invasive; small incisions) may replace open thoracotomy (larger incision). Two standard chest tubes are placed at the end of the operation. Postoperative patients will be monitored on the intensive care unit for at least 12 hours.

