3.2 End of Treatment

End of Treatment is defined as 6 weeks post surgery (approx. 4 weeks post discharge). In patients who discontinue during the treatment phase, an End of Treatment (EOT) visit will be performed within 28 days after treatment discontinuation.

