5.2.3 Pre-surgical visit

Tumor measurement	See section 5.1.1
according to RECIST 1.1	
(CT or MRI)	
Tumor assessments	Whole body PET-CT
CT or MRI	
Cardiac evaluation	12-lead ECG
Physical examination and	 Physical examination
vital signs	○ weight
	\circ Vital signs measurements will include body
	temperature, pulse and blood pressure
ECOG performance status	See Appendix 1 – ECOG Performance Status
Serum pregnancy test	A serum pregnancy test will be performed in pre-
	menopausal women and women who are
	menopausal for < 2 years if clinically indicated.
Lung function	Body plethymography / blood gas values
Hematology	Hemoglobin, erythrocytes, platelets, leukocytes,
	absolute neutrophils (ANC), basophils, eosinophils,
	lymphocytes, monocytes
Clinical chemistry +	Sodium, potassium, calcium, magnesium,
coagulation	phosphate, AST, ALT, PTT/INR, LDH, total bilirubin,
	albumin, creatinine, creatinine clearance (see
	section 18.4 Appendix 4), TSH
Concomitant medication,	Assessed on an ongoing basis
Adverse events	

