5.2.4 Discharge visit

Hematology	Hemoglobin, erythrocytes, platelets, leukocytes,
	absolute neutrophils (ANC), basophils, eosinophils,
	lymphocytes, monocytes
Clinical chemistry +	Sodium, potassium, calcium, magnesium,
coagulation	phosphate, AST, ALT, PTT/INR, LDH, total
	bilirubin, creatinine, creatinine clearance (see
	section 18.4 Appendix 4), TSH
Concomitant medication,	Assessed on an ongoing basis + peri-operative
Adverse events	complications
Post-op. tumor tissue	Regression grading accord. to Junker criteria (see
analysis	section 18.3 Appendix 3)

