5.2.5 End of Treatment Visit

Cardiac evaluation	12-lead ECG	
Physical examination and	 Physical examination 	
vital signs	o weight	
	 Vital signs measurements will include body 	
	temperature, pulse and blood pressure	
ECOG performance status	See Appendix 1 – ECOG Performance Status	
Lung function	Body plethymography / blood gas values	
Hematology	Hemoglobin, erythrocytes, platelets, leukocytes,	
	absolute neutrophils (ANC), basophils, eosinophils,	
	lymphocytes, monocytes	
Clinical chemistry +	Sodium, potassium, calcium, magnesium,	
coagulation	phosphate, AST, ALT, PTT/INR, LDH, total bilirubin,	
	albumin, creatinine, creatinine clearance (see	
	section 18.4 Appendix 4), TSH	
Concomitant medication,	Including peri-operative complications	
Adverse events		

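### A patient taken off pembrolizumab for toxicity after dose 1 has no scheduled post-treatment imaging or regression grading, even if resected

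*Protocol*

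**What the plan says.** **Stopping the drug.** Table 1 in protocol 6.3.1 requires permanent discontinuation for several events possible after one dose, such as Grade 3-4 pneumonitis, nephritis or infusion reaction. Its note adds: "Permanently discontinue for any severe or Grade 3 drug-related AE that recurs or any" life-threatening event. Neither the table nor the text of 6.3.1 mentions surgery.

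**What follows.** Section 3 gives pembrolizumab "for 2 cycles or occurrence of non-tolerable toxicity. After completion of immunotherapy lobectomy or bilobectomy with curative intent is scheduled". Section 3.1 says that if progression or "non-tolerable toxicity is noted during immunotherapy, an End of Treatment (EOT) visit will be performed and the patient will enter the follow-up phase". Section 3.2 puts the usual EOT visit 6 weeks after surgery, but adds: "In patients who discontinue during the treatment phase, an End of Treatment (EOT) visit will be performed within 28 days after treatment discontinuation". Section 5.3, on premature discontinuation, names only the EOT and follow-up investigations. Section 3.1.1 says: "Surgery is the standard treatment in the neoadjuvant treatment approach and not a study specific procedure".

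**Where the response data come from.** The pre-surgical visit (5.2.3) has the RECIST measurement and "Whole body PET-CT". The discharge visit (5.2.4) has "Regression grading accord. to Junker criteria". The EOT visit (5.2.5) lists neither.

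**Analysis.** Protocol 8.3.2 and SAP 2.9 require a documented tumor assessment after treatment start for the PP set. SAP 5 analyses efficacy primarily in that set and repeats it in ITT. SAP 2.8 works on available data, with an exception for response rates that refers to SAP 5.2.

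**The concern.** Radiologic response and pathologic regression are both part of the primary endpoint (protocol 2.4). A patient who stops after dose 1 because of toxicity may well still be resected, since surgery is standard care. The tumor would then be available for grading and a pre-operative scan would be possible. On the route that 3.1, 3.2 and 5.3 describe, the study schedules neither.

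The missing data would be linked to drug toxicity, so the remaining patients would be a selected group. Peri-operative safety after immunotherapy is also something the trial sets out to learn (protocol 1.4), and these patients are among the most informative on it.

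**Working it through.** **Step 1. The two routes for a patient stopped after dose 1.**

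| Item | 3.1, 3.2 and 5.3 | Section 3 read as keeping surgery on study |
|---|---|---|
| Post-treatment PET-CT and RECIST | not scheduled | pre-surgical visit |
| Junker grading | not scheduled | discharge visit |
| EOT visit | within 28 days of stopping | 6 weeks after surgery |
| PP set | excluded, unless a scan is documented outside the schedule | can be included (one dose is enough) |
| End of non-serious AE recording | unclear | 6 weeks after surgery |

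Three sections support the first route. One overview sentence can be read the second way. The trigger in sections 3 and 3.1, non-tolerable toxicity, is not defined or tied to Table 1.

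**Step 2. Does the ITT repeat recover these patients?** SAP 2.8 does not impute. Its exception says that missing response assessments are taken into account as set out in SAP 5.2. SAP 5.2 defines DFS, OS, incomplete dates and change in tumor size, and has no rule for a missing response. No rule exists for Junker grading either. The ITT tables therefore fall back on available data. (Change in SUV is outside the SAP altogether, per SAP 1.3.1.)

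**Step 3. Adverse event window.** Protocol 7.5.1 records AEs to 6 weeks after surgery and equates that time with the EOT visit. If the stop is decided at V2 (Day 21 ± 3), the 28-day limit gives:

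- earliest: 18 + 28 = Day 46
- nominal: 21 + 28 = Day 49
- latest: 24 + 28 = Day 52

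Planned discharge is Day 60-74, so this EOT visit falls before it and the two anchors in 7.5.1 disagree. SAEs are less exposed, because 7.5.1 generally records them to 90 days after the last dose.

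**Step 4. How many patients.** The documents give no stop rate for a two-dose course. Protocol 1.2.4 reports that 11.9% discontinued for an AE across monotherapy trials. A stop between two doses should be rarer, so I take 11.9% as the upper end and 2% as an assumed lower end.

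- Expected number: 30 × 0.02 = 0.6; 30 × 0.119 = 3.57, about 3.6
- Chance of at least one, with patients independent: 1 − 0.98^30 = 45%; 1 − 0.881^30 = 98%

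**Step 5. Effect on pathologic response.** Table 3 gives 43% with an exact interval of 25.2-62.3. This reproduces: Clopper-Pearson with 0.43 × 30 = 12.9 events in 30 gives 25.2% to 62.3%. Take the nearest whole count, 13/30 = 43.3%, and leave k patients ungraded. The estimate runs from (13 − k)/(30 − k), if all k were responders, to 13/(30 − k), if none was.

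| k | All responders | None a responder |
|---|---|---|
| 1 | 12/29 = 41.4% | 13/29 = 44.8% |
| 4 | 9/26 = 34.6% | 13/26 = 50.0% |

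**The case against.** The best reply is that the plan does give an answer. Sections 3.1, 3.2 and 5.3 agree on EOT and follow-up, and section 3 ties resection to completing immunotherapy. A reader might infer that the protocol leaves such patients without direction, or denies them surgery. The documents support neither: the on-study route is stated three times, and surgery remains standard care. What stands is that the stated route omits the response assessments.

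A reader might also infer that non-serious peri-operative AEs will be lost. That goes too far. Taken literally, 7.5.1 runs to 6 weeks after surgery, and SAP listing 16.2.4.16 has a field for post-operative complications. The Day 46-52 result also assumes that the stop is decided at V2. Table 1 allows toxicity up to 12 weeks from the last dose to resolve, so the decision may come later, and Day 60-74 is the calendar for patients who had both doses. The end of recording is unclear; loss is not established.

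The size can fairly be challenged. The 2% has no source and the 11.9% comes from trials of any duration. Some patients stopped for severe toxicity would be unfit for surgery and ungraded on either route. The k = 4 extremes need all four patients to have the same outcome. One ungraded patient shifts the estimate by about 2 points at most, against a planned interval of 25.2-62.3 in a descriptive pilot.

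Finally, Table 1 may seem to contradict itself on endocrine events. Hypothyroidism is in the hold column, but both action cells say to continue on replacement. The note's reference to any life-threatening event can be read as overriding the rows. I draw nothing from either.

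**Conclusion.** The point holds as a gap in data collection. Followed as written, 3.1, 3.2 and 5.3 leave a patient stopped after dose 1 without scheduled post-treatment imaging or regression grading, even when the tumor is resected. The PP rule then removes that patient from the main efficacy analysis, and the SAP has no rule that restores the patient in ITT. The loss is selective, because it depends on tolerating dose 1.

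The effect is probably small: about one to four patients at most plausible rates, possibly none, resting on the assumed 2% to 11.9%. It should not be read as proof that the response endpoints are biased. The documents do not say whether patients with early toxicity respond better or worse, so the direction is unknown. The change is worth making because it is cheap and protects primary endpoint data in a trial of 30 patients.

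**What to change.** Add to protocol 3.1, 5.3 and 6.3.1: *Stopping pembrolizumab for toxicity does not end the surgical part of the study. Patients who remain resectable have the pre-surgery visit with PET-CT and RECIST, surgery once the toxicity has sufficiently resolved, the discharge visit with Junker grading, and the EOT visit 6 weeks after surgery, with AE recording until then.*

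Add to 3.2: *The 28-day EOT visit applies only to patients who will not have surgery.*

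Section 5.3 must be included, or it would still name only the EOT and follow-up investigations and conflict with the new text.

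The cost is a short amendment and retraining at one site. The visits are those already scheduled for every resected patient. The downside is a pre-surgery PET-CT and a later EOT visit for a few patients. The amendment does not supply the response-rate rule missing from SAP 5.2, which would still be needed for patients who never reach surgery.
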